### Section II: Guidance for Assessment of Potential Etiology

Questions to Assess Etiology

Investigate potential causes for the subject's elevated liver enzymes using the questions below. Answers to the questions should be recorded in the subject's source documents and appropriate eCRFs.

- 1. Has the subject recently:
  - Had a change in his/her pattern of alcohol use? Investigate historic pattern of alcohol use as well.
  - Administered an illegal drug(s) (including intravenous drugs)?
  - Been exposed to a chemical agent or other environmental toxin?
  - Consumed any unusual foods (e.g., mushrooms), seasonal foods, or initiated treatment with new herbal/nutritional supplements?
  - Initiated a new diet regimen, started a rigorous exercise program, or experienced any form of severe physical exertion?
  - Traveled to another country or region?
- 2. Does the subject have a relevant concomitant illness (e.g., cholelithiasis, hepatitis, etc.) or has the subject had potential exposure to viral hepatitis (transfusion, tattoo, new sexual partner)?

**Protocol/Amendment No.:** 002-01

3. Does the subject have a relevant medical history (e.g., autoimmune disorder, cancer, Gilbert's syndrome, obesity, Wilson's disease, NASH, alcoholic or infectious hepatitis, biliary tract disease, hypoxic/ischemic hepatopathy, etc.)?

4. Has the subject recently been treated with a concomitant medication(s) with demonstrated or suspected effects on the liver (e.g., acetaminophen; amiodarone; aspirin; chlorpromazine; dantrolene; erythromycin; halothane; isoniazid; methyldopa; nitrofurantoin; oxyphenisatin; perhexiline maleate; phenytoin; propylthiouracil; rifampin; sulfonamides; tetracyclines) or initiated treatment with another new medication(s)?

### Additional Laboratory/Imaging Evaluations

In subjects for whom an etiology for the abnormal liver enzymes is unknown or whose elevated liver enzymes persist for more than 1-week:

- 1. Consider performing serologic tests including: (a) Hepatitis A (IgM); (b) Hepatitis B (surface antigen and core IgM); (c) Hepatitis C (antibody); (d) Hepatitis E (IgG and IgM). Obtain consent prior to testing, if required locally. Additional evaluations may be performed at the discretion of the investigator.
- 2. Consider an ultrasound of the subject's right upper quadrant and additional scans (endoscopic retrograde cholangiopancreatography [ERCP] or magnetic resonance cholangiopancreatography [MRCP]) if needed.

**Note**: Subjects may also be referred to a gastroenterologist or hepatologist for an additional work-up if considered necessary by the investigator.

**Protocol/Amendment No.:** 002-01

# 12.6 Predefined Limits of Change (PDLC)

The following predefined limits of change will be assessed in the statistical analysis, as described in Section 8.2.4.2.

			Categories Assessed for Each Criterion	
		At Least One	Last On-	
Laboratory Test	Predefined Limits of Change † Criterion	Value	Treatment Value	
	Laboratory – Hematology			
Hemoglobin (g/dL)	1. Decrease ≥1.5 g/dL	Y	Y	
	2. Increase >2.0 g/dL	Y	Y	
	3. Increase >2.0 g/dL and value > ULN	Y	Y	
WBC Count (10  /microL)	1. Decrease ≥50% and value < LLN	Y	Y	
	2. Increase ≥20% and value > ULN	Y	Y	
Neutrophil Count (10  /microL)	1. Decrease ≥20% and value < LLN	Y	Y	
	2. Increase ≥20% and value > ULN	Y	Y	
Lymphocyte Count (10  /microL)	1. Decrease ≥20% and value < LLN	Y	Y	
	2. Increase ≥20% and value > ULN	Y Y	Y	
Platelet Count (10  /microL)	1. Decrease ≥25% and value < LLN	Y	Y	
	2. Increase ≥100% and value > ULN	Y	Y	
	Laboratory – Chemistry			
BUN (mg/dL)	1. Increase ≥50% and value > ULN	Y	Y	
eGFR	1. Decrease > 30%	Y	Y	
	2. Decrease > 50%	Y	Y	
Total Bilirubin (mg/dL)	1. Value >2x ULN	Y	Y	
AST (IU/L)	1. Value ≥3x ULN	Y	Y	
, , ,	2. Value >5x ULN	Y	Y	
	3. Value >10x ULN	Y	Y	
	4. Value >20x ULN	Y	Y	
ALT (IU/L)	1. Value ≥3x ULN	Y	Y	
	2. Value >5x ULN	Y	Y	
	3. Value >10x ULN	Y	Y	
	4. Value >20x ULN	Y	Y	
AST (IU/L) or ALT (IU/L)	1. Value ≥3x ULN	Y	Y	
	2. Value >5x ULN	Y	Y	
	3. Value >10x ULN	Y	Y	
	4. Value >20x ULN	Y	Y	
AST (IU/L) or ALT (IU/L)+ Total	1. ALT ≥3× ULN or AST ≥3× ULN with	Y	Y	
Bilirubin (mg/dL)	concurrent Bilirubin >2× ULN			
Alkaline Phosphatase (IU/L)	1. Value >1.5x ULN	Y	Y	
Serum Uric Acid (mg/dL)	1. Increase ≥50% and value > ULN	Y	Y	
Serum Sodium (mEq/L)	1. Decrease ≥10 mEq/L and value < LLN	Y	Y	
	2. Increase ≥10 mEq/L and value > ULN	Y	Y	
	3. Value $> 155 \text{ mEq/L}$	Y	Y	
Serum Potassium (mEq/L)	1. Decrease ≥1.0 mEq/L and value < LLN	Y	Y	
`	2. Increase ≥1.0 mEq/L and value > ULN	Y	Y	
	3. Value >5.4 mEq/L and value increased by	Y	Y	
	15%.above baseline			
	4. Value $\geq$ 6.0 mEq/L	Y	Y	
Serum Calcium (mg/dL)	1. Increase ≥1.0 mg/dL and value > ULN	Y	Y	
	2. Decrease ≥1.0 mg/dL and value < LLN			

**Protocol/Amendment No.:** 002-01

ECG			
Serum Magnesium	
 
Increase ≥1.0 mg/dL and value > ULN
 
Decrease ≥1.0 mg/dL and value < LLN
 
	Y	Y
Serum Phosphate	
 
Increase ≥0.5 mg/dL and value > ULN
 
Decrease ≥0.5 mg/dL and value < LLN
 
	Y	Y
QTc (milliseconds)	1. ≥500 msec	N	Y
	1. Increase ≥30 msec and value above gender specific ULN ¶	N	Y
	2. Increase ≥60 msec and value above gender specific ULN ¶	N	Y

† Increases and decreases are relative to baseline.

"At Least One Value" will include results meeting the PDLC criterion at any time during the Treatment Period (defined as the period from randomization up to 2 days after the final dose of study medication). "Last On-treatment Value" will include only the last available result during the Treatment Period. A listing of all post Treatment Period values that meet PDLC criteria will also be provided.

04T4BY

‡ LLN = Lower limit of normal.

§ ULN = Upper limit of normal.

¶ 430 msec and 450 msec for males and females, respectively.

**Protocol/Amendment No.:** 002-01

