# 8.2.3.2 Statistical Methods for Safety Analyses

Safety and tolerability will be assessed by clinical review of all relevant parameters including AEs, laboratory tests, vital signs and ECGs.

Safety analyses will be performed for three time periods: Week 0 to Week 52 (Phase A), Week 52 to Week 104 (Phase B), and Week 0 to Week 104 (Phase A+B). Phase A is considered the primary time period for safety evaluation. All safety endpoints will be analyzed for the Phase A and Phase A+B time periods. For the Phase B time period, only AEs and PDLC in laboratory parameters will be analyzed. The population for analyses of only Phase B will be all subjects who took at least one dose of study medication in Phase B.

Two sets of data will be considered: data pertaining to the Treatment Period and data pertaining to all post-randomization follow-up. For AEs, the Treatment Period dataset will include all data from randomization to 14 days after the final dose of study medication, with the exception of analyses of the Phase A Treatment Period, for which the 14 additional follow-up days will be included only for subjects who did not continue into Phase B. For laboratory endpoints, the Treatment Period dataset will include all data from randomization to 2 days after the final dose of study medication. The "all post-randomization follow-up" dataset, which applies only to SAEs, will include all data after randomization, with no upper limit on the follow-up window. Listings of AEs (regardless of seriousness) and of PDLCs occurring beyond the Treatment Period will be provided. Laboratory data collected after the Treatment Period will be summarized separately from Treatment Period data.

**Protocol/Amendment No.:** 002-01

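### The three QTc limits are counted only on the last on-treatment ECG, so the 104-week table omits a Week 52 exceedance followed by a normal on-treatment ECG, although the Phase A table normally counts it

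*Combined protocol and SAP*

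**What the plan says.** Section 12.6 gives each predefined limit of change (PDLC) two possible counting categories.

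- At Least One Value: "will include results meeting the PDLC criterion at any time during the Treatment Period".
- Last On-Treatment Value: "will include only the last available result during the Treatment Period".

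The Treatment Period for this purpose is "the period from randomization up to 2 days after the final dose of study medication".

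The laboratory criteria with legible flags are marked Y in both columns. The QTc rows are marked N, then Y. The first reads "QTc (milliseconds) 1. ≥500 msec N Y". The two increase criteria (at least 30 msec, and "Increase ≥60 msec and value above gender specific ULN") carry the same flags. No reason is given for the difference.

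On reporting, Section 12.6 adds: "A listing of all post Treatment Period values that meet PDLC criteria will also be provided". Section 8.2.3.2 states "All safety endpoints will be analyzed for the Phase A and Phase A+B time periods", and also "Phase A is considered the primary time period for safety evaluation".

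The Section 6.0 flow chart schedules ECGs at Week -2, Day 1, Week 52, Week 104 and the Discontinuation Visit. None is scheduled at the Rescue Visit.

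**The concern.** A QTc threshold count is normally read as the number of subjects who ever crossed the threshold on treatment. Over 104 weeks a completer has two scheduled post-randomization ECGs, and the last-value rule uses only the second. A reader of the Phase A+B table would take it to cover the whole period, whereas for completers it reports the state at Week 104.

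The other planned outputs do not give the missing 104-week count. The PDLC listing starts where the Treatment Period ends. The remaining ECG output in Section 8.2.3.2 is a Tier 3 summary of continuous change, which does not count subjects over a limit.

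**Working it through.** The plan states no QTc rate or expected count, so there is no figure to reproduce. The check has two parts: following one subject through the rules, then an illustration of size.

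**One subject.** Take QTc ≥500 msec at Week 52 and a normal QTc at Week 104, the latter within 2 days of the last dose.

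| Output | Value used | Counted or shown? |
|---|---|---|
| Phase A PDLC table | Week 52, the only scheduled post-randomization ECG in Phase A for a subject who continues | Yes |
| Phase A+B PDLC table | Week 104 | No |
| PDLC listing | Post-Treatment-Period values only | No |
| Continuous ECG summary | Enters the Week 52 mean | Not as a threshold case |

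Two variations matter. If the later ECG is a discontinuation ECG more than 2 days after the last dose, it falls outside the Treatment Period; Week 52 remains the last on-treatment value and the subject is counted in Phase A+B. If a normal unscheduled ECG follows the abnormal one within Phase A, which Section 7.1 permits when clinically necessary, the same rule removes the subject from the Phase A table too.

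**Size, under stated assumptions.** Let p be the probability of an exceedance at each ECG, equal at both. Let k be persistence from 0 (independent) to 1 (always persists), and c the probability of exceeding at Week 104 given an exceedance at Week 52.

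- c = p + k(1 − p)
- Last-value proportion = p
- Any-value proportion = p + p(1 − c)
- Share of affected subjects missed = (1 − c)/(2 − c)

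For expected counts, take n per arm from Section 8.2.6: 410 × (1 − 0.312) = 282. This ignores attrition after Week 52, which would shrink both counts but not the share. Both p and k are assumed.

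| p | k | Last value, n·p | Any value, n·[p + p(1 − c)] | Share missed |
|---|---|---|---|---|
| 0.5% | 0 | 1.4 | 2.8 | 50% |
| 0.5% | 0.5 | 1.4 | 2.1 | 33% |
| 0.5% | 1 | 1.4 | 1.4 | 0% |
| 1% | 0 | 2.8 | 5.6 | 50% |
| 1% | 0.5 | 2.8 | 4.2 | 33% |
| 1% | 1 | 2.8 | 2.8 | 0% |

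Worked line for p = 1%, k = 0.5: c = 0.01 + 0.5 × 0.99 = 0.505; any-value proportion = 0.01 + 0.01 × 0.495 = 0.01495; 282 × 0.01495 = 4.2; share missed = 0.495/1.495 = 33%.

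The share depends almost entirely on k. Section 8.2.3.2 and Table 13 show a between-group confidence interval for a PDLC only when at least 4 subjects in some group meet it. At p = 1% and k up to 0.5, the expected count lies below 4 under last value and above 4 under any value. If QTc limits are tiered like the other PDLCs, the counting rule could therefore decide whether an interval is shown.

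**The case against.** The best defence is that the flags are set criterion by criterion and may be deliberate. Chemistry is measured at nearly every visit, so any and last differ greatly there. ECGs are taken about once per phase, and on scheduled ECGs the two categories coincide in Phase A. Phase A is the primary safety period and has its own study report. An exceedance at Week 104, or at discontinuation in Phase B within the 2-day window, is counted in the Phase A+B table. So every exceedance on a scheduled on-treatment ECG is counted in one table or the other, unless an unscheduled normal repeat displaces it. Subjects rescued in Phase A do not enter Phase B, so they normally have no later scheduled ECG to overwrite an earlier one. Individual detection does not rest on this table either: Section 7.1.2.7 requires site review of post-randomization ECGs as well as the central reading.

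All of that stands, and it limits the consequence. It does not justify the rule for Phase A+B, where completers have two ECGs and no single output counts subjects who met a limit at either.

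A reader might also infer that abnormal ECGs are the ones most likely to be repeated, so that Phase A is systematically under-counted as well. The documents do not support this. Section 7.1.2.7 specifies single ECGs, and the protocol has no rule for repeating an abnormal one. An unscheduled repeat is possible, but its frequency is unknown.

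**Conclusion.** The point holds for the Phase A+B PDLC table and is minor. That table omits subjects who met a QTc limit at Week 52 and had a later normal ECG within the Treatment Period, and the planned listing does not recover them.

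Two stronger readings go too far. The first is that a Week 52 exceedance disappears from safety reporting; it is counted in the primary Phase A table unless a normal unscheduled repeat follows within that phase. The second is that half the cases are lost. About 50% is the upper end, reached only if two ECGs in the same person are independent. With equal rates at the two ECGs the range is 0% to about 50%, and nothing in the documents locates the truth within it.

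The direction within each arm is certain: an any-value count is never smaller than a last-value count. How a between-arm difference would move is not determined.

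**What to change.** In Section 12.6, change N to Y under At Least One Value for all three QTc criteria and report both columns, as for the laboratory tests. The change is three table cells and one further column of output. Post-randomization ECGs are already read centrally (Section 7.1.2.7), so no visit, procedure or data item is added. Section 8.2 provides for changes to non-confirmatory analyses to be listed and explained in the study report; this one is best made before the Phase A unblinding.

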# 12.7 Mapping of Relative Day Ranges to Weeks

The following rules, applicable to all endpoints that (per the study flow chart) are scheduled for collection at all of the time points in the final column below, will be used to map the relative day ranges to weeks, as described in Section 8.2.

Mapping of Relative Day Ranges to Weeks

Required Phase	Relative Day Range	Week	
	Visit and/or Day Relative to Start of Trial		
_	Visit <2 and Day <1	$min(Day/7^{\dagger}, -2)$	
Placebo Run-in	Visit ≥2 and Day <1	-2	
Placebo Run-in	Visit ≥3 and Day ≤1	0	
A	2 ≤ Day ≤63	6	
A	$64 \le \text{Day} \le 105$	12	
A	$106 \le \text{Day} \le 154$	18	
A	$155 \le \text{Day} \le 228$	26	
A	229≤ Day ≤ 319	39	
A	320 ≤ Day	52	
	Day Relative to the Start of Phase B		
В	$1 \le \text{Day} \le 137$	65	
В	$138 \le \text{Day} \le 228$	78	
В	$229 \le \text{Day} \le 319$	91	
В	320 ≤ Day	104	
† Truncated to the largest integer less than or equal to this ratio.			

If there are multiple values in the same day range, the last value within that day range will be used for the analysis.

For endpoints that are scheduled to be collected at fewer post-randomization time points, analogous logic to that used above will be applied. For example, Week 26, Week 52, and Week 104 are the only scheduled time points for collection of lipid panel endpoints. The day range for Week 26 will begin at Day 2 and continue until Day 273 (midpoint between 26 weeks and 52 weeks), and the day range for Week 52 will include all Phase A data after Day 273. The day range for Week 104 will include all days within Phase B.

Protocol/Amendment No.: 002-01

#### 12.8 SAS Code for cLDA Model

Sample SAS code for fitting cLDA model are provided below. This serves as an example only, not the actual implementation codes for this trial. The sample code below assumes that there is a baseline and 4 post-baseline measurements (Weeks 6, 12, 18 and 26) and 2 treatment groups (MK-8835 and placebo).

```
*******************************
** data step necessary prior to running SAS PROC MIXED;
*******************************
DATA long; SET long;
ARRAY T{5} t0-t4; * time indicator variables;
ARRAY TT{5} tt0-tt4; * time by treatment indicator variables;
** define week times treatment indicator variables:
DO i = 1 TO 5;
t\{i\} = (time=(i-1));
tt\{i\} = t\{i\}*(trt=1);
END;
DROP i;
RUN:
*************************
** fitting the cLDA model using SAS PROC MIXED;
********************
PROC MIXED DATA=long;
CLASS subj time; ** subj is the subject id number **;
MODEL y=time tt1 tt2 tt3 tt4;
REPEATED time / SUBJECT=subj TYPE=UN;
ESTIMATE 'T1 Diff (MK-8835-Placebo)' tt1 1;
ESTIMATE 'T2 Diff (MK-8835-Placebo)' tt2 1;
ESTIMATE 'T3 Diff (MK-8835-Placebo)' tt3 1;
ESTIMATE 'T4 Diff (MK-8835-Placebo)' tt4 1;
ESTIMATE 'T1 Placebo LSM' time -1 1 0 0 0;
ESTIMATE 'T2 Placebo LSM' time -1 0 1 0 0:
ESTIMATE 'T3 Placebo LSM' time -1 0 0 1 0;
ESTIMATE 'T4 Placebo LSM' time -1 0 0 0 1;
ESTIMATE 'T1 MK-8835LSM' time -1 1 0 0 0 tt1 1;
ESTIMATE 'T2 MK-8835LSM' time -1 0 1 0 0 tt2 1;
ESTIMATE 'T3 MK-8835LSM' time -1 0 0 1 0 tt3 1;
ESTIMATE 'T4 MK-8835LSM' time -1 0 0 0 1 tt4 1;
ODS OUTPUT Estimates=outm1;
RUN;
```

Protocol/Amendment No.: 002-01

